3.2 Secondary Objectives

The following secondary objectives will be used to support the results of the primary objective:

1. Assess independent effects of three active concentrations of marijuana and placebo in reducing self-reported symptoms of PTSD with the PCL-5, anxiety and depression with the IDAS, and improving psychosocial functioning with the IPF and WBR (self-report and observer) among veterans during Stage 1.
2. Assess independent effects of three active concentrations of marijuana and placebo in reducing self-reported symptoms of PTSD with PCL-5, anxiety and depression with IDAS, and improving psychosocial functioning with the IPF and WBR (self-report and observer) among veterans during Stage 2.
3. Assess comparative efficacy between placebo and each active dose of marijuana based on a within-subjects analysis of PTSD symptoms as measured by the CAPS-5 in crossover participants at Baseline, End of Stage 1, Stage 2 Baseline, and End of Stage 2.
4. Assess whether Stage 2 crossover participants' preferences for marijuana concentrations in Stage 1 and Stage 2 correlate with reduction in PTSD symptoms as measured by the CAPS-5 total score.
5. Assess whether participants experience a clinically significant increase in PTSD symptoms based on CAPS-5 and PCL-5 total scores during the washout period between Stage 1 and Stage 2 compared with measures assessed at Baseline and during Stage 1.
6. Explore correlation of treatment outcomes measured by CAPS-5 score with objective changes in sleep via Actigraphy throughout the study and self-reported

- changes in sleep quality using the ISI on a weekly basis.
7. Explore correlation of Daily Diary items related to sleep with objective changes in sleep via Actigraphy and self-reported changes in sleep quality using the ISI on a weekly basis.
 8. Explore correlation of treatment effects measured by CAPS-5 total score with amount of marijuana used based on Daily Diary across Stage 1 and Stage 2.
 9. Explore treatment outcomes measured by CAPS-5 total score by marijuana concentration, with concomitant substance and medication use as a covariate throughout the treatment period.
 10. Explore durability of treatment outcomes measured by CAPS-5 total score, with any PTSD treatments based on the LTFU questionnaire treated as a covariate, six months after completing Stage 2.

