3.4 Process Objectives

The following objectives will include exploratory analyses intended to inform future studies:

1. Evaluate protocol compliance based on comparison of Daily Diary entries, including information on amount, time and frequency of marijuana use, and the weight of any unused marijuana across each study stage.
2. Evaluate protocol compliance using quantitative blood and/or urine cannabinoid levels.
3. Evaluate whether markers of inflammation CRP, IL-1 β , and IL-6 levels in blood predict PTSD severity at baseline and treatment outcome as a function of marijuana concentration.
4. Assess the ability of site staff and participants to accurately guess condition assignment in Stage 1 and Stage 2.

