 - m) Perform a urine-dip EtG test on all participants to assess alcohol consumption.
 - n) Identical weekly evaluations like this will occur until the next cessation period.

5.2.9 Primary and Secondary Endpoint Evaluations in Stage 1 (Visit 5) and Stage 2 (Visit 12)

This visit will be conducted at the end of self-administration in each stage. This meeting will take place in person, via telemedicine or phone. This visit may take place on the same day as Visit 6 or Visit 13 (Day 1 of cessation in Stage 1 or Stage 2).

- a) Participants will meet with the IR for a 60 to 90 minute evaluation.
- b) The IR will administer the last month CAPS-5.

5.2.10 Two Weeks of Abstinence from Marijuana Self-Administration during Cessation 1 (Visit 6) and Cessation 2 (Visit 13)

Participants will cease to self-administer marijuana for a two-week interval. After a face-to-face visit, participants will complete a telephone contact and self-report measures one week after the start of cessation. The Daily Diary will continue to be completed daily.

- a) At the start of the Cessation period, immediately after completion of the primary/secondary endpoint assessment, participants will visit the study site. This

- visit may be conducted on the same day as the endpoint assessment or within two days of it.
- b) The participant will complete the IDAS, ISI, IPF, WBR, PCL-5 and the MWC.
 - c) Site staff will contact the community observer for completion of the WBR.
 - d) The CI or qualified designee will administer the C-SSRS and GWB.
 - e) The participant and a blinded site staff member will provide their belief of condition assignment.
 - c) Inquire about any possible changes in the participant's health to ensure they continue to meet eligibility criteria.
 - d) Collect information on any changes in psychotherapy, health or medications for the participant.
 - e) Obtain vital signs from the participant.
 - f) Obtain a urine sample to test drugs of abuse. Participants of childbearing potential will have a pregnancy test performed.
 - g) Participants will return any unused marijuana in the original package dated by day of use from the last week of self-administration. Any unused marijuana from each weekly allotment will be returned to the CI or designee to be weighed and accounted for. Marijuana will be labeled with the participant number and date. The remaining marijuana will be preserved and securely stored at the site until destruction per DEA instruction.

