 - h) Peripheral blood will be collected for:
 - Blood Cannabinoid analyses
 - Biomarker analyses
 - i) The participant will bring their portable tablet to the study site. The site staff will review all video recording files, noting the time and date. Upon receipt, site staff will verify participant identity, safety, and compliance through review of video recordings, as well as telephone contact reports. Upon review, if any days are missing from recordings, participants will be re-trained by site staff. The portable device will be cleared of content and returned to the participant.
 - j) The participant will bring their Actigraph to the study site. The site staff will copy all recording files, note the time and date stamp and save for analysis. The Actigraph memory will be cleared, the device charged and returned to the participant to use for the next week. Upon analysis, if any days are missing from recordings, participants will be re-trained the next time they are contacted by site staff.
 - k) The site staff will instruct the participant to complete the Daily Diary to assess, sleep patterns, continuing substance and medication use patterns and AEs during cessation.
 - l) The site staff and participant will discuss the two-week period of cessation of marijuana use.
 - m) One week after the beginning of cessation, participants will complete the MWC , IDAS, ISI, IPF, WBR, and PCL-5 electronically. Participants will be reminded to complete self-report measures in a timely manner.
 - n) One week after the beginning of cessation the CI or site staff will telephone the community observer to complete the WBR assessment.

5.2.11 Re-Baseline Evaluation at end of Cessation 1 (Visit 7) and Cessation 2 (Visit 14)

At the end of the Cessation period, two weeks after completion of the primary/secondary endpoint assessment, participants will visit the study site.

- a) The participant will complete the IDAS, ISI, IPF (past 2 weeks), WBR, PCL-5 and the MWC.
- b) The participant will complete the CUDIT-R only at Visit 14.
- c) Site staff will contact the community observer for completion of the WBR.
- d) The CI or qualified site staff will administer the C-SSRS and GWB.
- e) Participants will meet with the IR for a 60 to 90 minute evaluation, either in a face-to-face or telemedicine meeting to administer the last week CAPS-5.

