- f) During the site visit, site staff will inquire about any possible changes in the participant's health to ensure they continue to meet eligibility criteria.
- g) Collect information on any changes in psychotherapy, AEs or medications for the participant.
- h) Obtain vital signs from the participant.
- i) Obtain a urine sample to test drugs of abuse.
- j) Females of childbearing potential will have a pregnancy test performed.
- k) The participant will bring their Actigraph to the study site. The site staff will copy all recording files, note the time and date stamp and save for analysis. Participants will not be given the Actigraph in Stage 3.
- l) The site staff will instruct the participant to complete the Daily Diary during upcoming self-administration through electronic patient reported outcomes (ePRO).
- m) Perform a urine-dip EtG test on all participants to assess alcohol consumption.
- n) Peripheral blood will be collected for:
 - Blood Cannabinoid levels analysis
 - Biomarker analyses
- o) After this assessment, participants will either continue in the crossover arm (Stage 2) with associated introductory sessions as described in Section 5.2.3, or they may continue to the optional Stage 3 as described in Section 5.2.9 if they have already completed Stage 2. Participants who do not continue to Stage 3 will be required to return the lockable storage box and portable tablet to site staff.

5.2.12 Stage 3

Stage 3 is an optional continuation of the study for participants who request the amount of returned marijuana from Stage 1 or Stage 2 to be issued from a new supply of marijuana. Site visits will be conducted weekly as needed to complete Stage 3, which will last up to two months or until remaining marijuana is consumed.

- a) The CI will dispense marijuana in the amount that was left over from Stage 1 or Stage 2 according to the participants randomization in Stage 1 and/or Stage 2 from a new supply if the participant requests to take part in Stage 3. Participants

- will be able to choose to receive a weekly kit containing the same blend of marijuana from a new supply as their Stage 1 or Stage 2 study product supply at each weekly visit.
- b) Participants will retain the locked storage box and portable tablet to be used for Daily Diary and DEQ completion as in Stage 1 and Stage 2 if they chose to participate in Stage 3.
 - c) Participants will be required to video record each self-administration on the same portable tablet.

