onset latency (SOL), and sleep efficiency (SE) entered as the repeated measure in independent analyses and group entered as the IV. An ITT approach will be used. Statistical significance will be set at $p = .05$ for all analyses.

Quantitative levels of THC, CBD and their metabolites will be assessed in order to ascertain whether participants comply with only using the marijuana assigned to them during the study. If there is sufficient data, correlational analyses may also be conducted between biological cannabinoid levels and clinical outcomes to determine whether there is a dose-response effect between cannabinoid exposure and clinical response.

Prognostic value of CRP, IL-1 β and Il-6 will be examined using two regression analyses, one between biomarker values gathered at Baseline and at the primary endpoint CAPS-5 global severity score, and another between biomarker values collected after two weeks of cessation and the CAPS-5 global severity score at the end of Stage 1.

Qualitative safety analyses will examine Daily Diaries with summary tables listing maximum severity and duration, concomitant medications/therapies, and AEs with frequencies and percentages tabulated overall and by concentration group. Spontaneously reported reactions will be separated from unexpected AEs during analysis and presented separately in summary tables. Statistical analyses will be conducted to evaluate safety and AEs by marijuana treatment condition and individual demographic characteristics (e.g. gender, history of cannabis use, concomitant medication/drug use, baseline CAPS-5 score).

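### The second biomarker regression is called prognostic, but its predictor is drawn about two weeks after the outcome it is meant to predict

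*Protocol*

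**What the plan says.** Process Objective 3 (Protocol Section 3.4) asks whether the three inflammation markers "predict PTSD severity at baseline and treatment outcome as a function of marijuana concentration". Section 3.4 describes its objectives as exploratory and meant to inform later studies.

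Section 12.0 turns this into an analysis of prognostic value. The markers "will be examined using two regression analyses, one between biomarker values gathered at Baseline and at the primary endpoint CAPS-5 global severity score", and the second regression is "another between biomarker values collected after two weeks of cessation and the CAPS-5 global severity score at the end of Stage 1".

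The visit descriptions fix when these quantities are measured. For the endpoint visits (Visits 5 and 12), Section 5.2.9 states: "This visit will be conducted at the end of self-administration in each stage". For the re-baseline visits (Visits 7 and 14), Section 5.2.11 states: "At the end of the Cessation period, two weeks after completion of the primary/secondary endpoint assessment, participants will visit the study site". The Section 5.2.11 visit includes a blood draw for biomarkers and a CAPS-5 with last-week recall.

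**The concern.** A prognostic analysis needs a predictor that is known before the outcome. Here the blood comes after the CAPS-5 score it is paired with. Between the two, the participant has stopped the assigned product and gone through two weeks of withdrawal.

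The marker may also have been changed by treatment. Section 2.2.2 attributes anti-inflammatory properties to both THC and CBD and proposes that these may mediate a treatment effect. On the protocol's own reasoning, then, a Visit 7 marker may reflect the assigned arm. An association with the earlier CAPS-5 could arise because symptoms influenced the marker, because treatment moved both, or because of withdrawal. None of these is prognosis. The trial is meant to inform larger ones, so an association filed under the prognostic label could mislead their design.

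**Working it through.** No sample-size or power figure is involved. The check sets the time of each draw against the time of each score.

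| Measurement | Visit | Time | Source (Protocol) |
|---|---|---|---|
| Baseline biomarkers and CAPS-5 (last month) | Screen 2 | before randomisation | Sections 5.2.3, 5.2.4 |
| End-of-Stage-1 CAPS-5 (last month) | Visit 5 | end of Week 3 | Section 5.2.9, Table 1 |
| Biomarkers at start of cessation | Visit 6 | same day as Visit 5 or within two days | Section 5.2.10 |
| Biomarkers and CAPS-5 (last week) after Cessation 1 | Visit 7 | end of Week 5 | Section 5.2.11, Table 1 |
| End-of-Stage-2 CAPS-5 (last month) | Visit 12 | end of Week 8 | Section 5.2.9, Table 1 |
| Biomarkers after Cessation 2 | Visit 14 | end of Week 10 | Section 5.2.11, Table 1 |

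**Which CAPS-5 is the outcome.** Secondary Objective 3 (Section 3.2) lists CAPS-5 "measured by the CAPS-5 in crossover participants at Baseline, End of Stage 1, Stage 2 Baseline, and End of Stage 2". End of Stage 1 and Stage 2 Baseline are separate time points there, and the primary analysis in Section 12.0 also uses the end of Stage 1 for its endpoint. The outcome is therefore the Visit 5 score.

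**Which draw is the predictor.** Lag = time of draw − time of outcome:

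- Visit 7: Week 5 − Week 3 = +2 weeks (about 14 days). The draw follows the outcome.
- Visit 14, if Cessation 2 were meant: Week 10 − Week 3 = +7 weeks. The draw follows the outcome by more.
- Screen 2, if the abstinence before enrolment were meant: the lag is negative, so the order is right. But Tables 1 to 3 place Screen 2 under Baseline, so this is the draw that the first regression already uses and the second would repeat it.

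Visit 7 is the only reading that gives a distinct Stage 1 analysis, and it has the wrong time order. The Visit 5 CAPS-5 asks about the last month, so the symptoms it scores lie further back still.

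**The first regression.** The Screen 2 draw precedes randomisation, and Visit 5 comes at the end of Week 3, so the predictor precedes the outcome.

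**A possible re-pairing.** Visit 7 biomarkers with the Visit 12 CAPS-5: Week 8 − Week 5 = 3 weeks, predictor first.

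**How precise an interaction could be.** With 19 per arm, a within-arm correlation on the Fisher z scale has standard error 1/√(19 − 3) = 0.25. The difference between two arms has standard error √(2 × 0.25²) = 0.354, so its 95% half-width is 1.96 × 0.354 = 0.69. Only very large differences between concentrations could be seen.

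**The case against.** The best defence is that the end of Stage 1 may mean the end of Cessation 1. Section 4.0 describes Stage 1 and its cessation together, Section 5.2.9 speaks of cessation as lying in a stage, and Section 12.0 uses different terms for the two outcomes within one sentence. A CAPS-5 is done at Visit 7 alongside the draw. This is the less natural reading: Section 2.1 puts cessation after each stage, and Section 3.2 separates the two scores. Even if it is accepted, the association is concurrent and not prognostic, so the label is still wrong.

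A second defence is that this is one exploratory analysis in a pilot. That stands, and it limits the weight of the point.

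A reader might also infer three stronger faults that the document does not support.

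- **That both regressions are fixed without concentration or baseline CAPS-5.** Section 12.0 names the pairs of variables and no covariates, but it does not say that the models are unadjusted. A statistical analysis plan, not shown here, could add the terms.
- **That leaving out the arm confounds the Baseline regression.** Baseline biomarkers precede randomisation and are independent of arm in expectation. Omitting the arm costs precision and leaves the by-concentration question unanswered, but it does not bias prognosis. The confounding worry applies only to a marker measured after treatment.
- **That the baseline-severity part of Process Objective 3 has been dropped.** The sentence describing the first regression is garbled about what is paired with what, and a further exploratory regression could sit in the analysis plan.

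**Conclusion.** The point holds for the second regression. As written, it pairs a Visit 7 marker with a Visit 5 score, about two weeks in the wrong direction, and calls the result prognostic. This affects one of the two planned biomarker regressions, for all three markers. Added covariates cannot repair it, because no adjustment lets a later measurement predict an earlier outcome.

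The conclusion rests on reading the end of Stage 1 as Visit 5 and the two weeks of cessation as Cessation 1. The alternative readings give a longer reversed lag, a concurrent association or a repeat of the first regression. None gives a separate prognostic analysis.

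The consequence is confined to an exploratory process objective. Nothing here touches the primary comparison, and the first biomarker regression has a sound time order.

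**What to change.** 1. Keep Baseline biomarkers predicting the Visit 5 CAPS-5 as the prognostic analysis of Stage 1, and clean up the sentence that describes it. State marijuana concentration and biomarker-by-concentration terms, because Process Objective 3 asks for prediction by concentration. Say in advance that the interaction will be imprecise at about 19 per arm.
2. Replace the second regression with one of these:
   - **A prognostic analysis for Stage 2.** Visit 7 biomarkers predict the Visit 12 CAPS-5, adjusted for the Visit 7 CAPS-5 and for both Stage 1 and Stage 2 assignment. Stage 1 assignment is needed because it determines which Stage 2 arms are open to a participant (Section 4.2) and its effects may carry over. Note that Visit 7 uses last-week recall and Visit 12 last-month recall. This answers a Stage 2 question, so the text should say so.
   - **A concurrent association, labelled as such.** Either Visit 6 biomarkers with the Visit 5 CAPS-5 (at most two days apart), or Visit 7 biomarkers with the Visit 7 CAPS-5.
3. Name visits, not stages, in the analysis text so that the pairing cannot be misread.

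The cost is wording in Section 12.0 and the matching analysis-plan text. Every draw and score named here is already in the schedule, so no visit or sample is added.

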AEs, including spontaneously reported reactions, will be collected as described in Section 8.0 of the protocol. Concomitant medications and therapies will be collected as described in Section 9.0 of the protocol.

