5.1.3 Process Measures

The Daily Diary is an instrument developed by the sponsor to track AEs and assess daily use of study marijuana as well as other substances. The Daily Diary will be an electronic data capture form completed on an electronic device. Information collected with this diary will include participants' self reported quality and duration of sleep, the daily amount of marijuana used concomitant use of alcohol, medications, or other drugs, as well as AEs. Daily diary reports will be confirmed and verified by phone contact, reviewing video of participants' self-administration of marijuana, and qualitative urine drug testing at the sites.

The LTFU questionnaire is a sponsor-developed self-report instrument that will gather information on current psychiatric health and wellbeing, including the occurrence of new traumatic events, and questions concerning the number and type of new treatments for PTSD the participant has undergone since his or her final visit during the treatment period. The LTFU questionnaire takes approximately five minutes to complete, and will be completed by the participants at the six-month follow-up.

Laboratory testing of blood/urine cannabinoids will be conducted by an accredited laboratory with an appropriately sensitive, specific and validated assay, as specified in Section 10.2. Peripheral blood samples will be collected and stored for biomarker analysis of cannabinoids (THC, 11-OH-THC, THC-COOH), CBD metabolites and inflammation markers with appropriately sensitive, specific and validated assays for CRP, IL-1 β , and IL-6. Peripheral blood will be drawn at specified times in the Time and Events Labs table and analyzed according to procedures described in Section 10.0.

Questions regarding the belief of condition assignment and certainty of the belief will be asked of site staff and participants at the End of Stage 1 and End of Stage 2. These beliefs are collected as a part of the sponsor's ongoing initiative to optimize the double-blind as a part of drug development studies.

Table 1: Time and Events (Administrative Procedures)

| | Screen | Baseline | | Stage 1 | | | Cessation 1 | | Stage 2 | | | Cessation 2 | | Stage 3 | LTFU |
|---------------------------------|---|----------------------------|--|---|---|--|-----------------------------------|---|--|---|---|-------------------------------------|---|-------------------------------------|--|

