8.3 Adverse Event Collection

AEs that will be collected during the protocol:

- SAEs will be collected through termination.
- All AEs will be collected from enrollment until end of the active study period (e.g. end of Cessation 2 or Stage 3, as applicable)
- Events requiring medical attention will be collected during the follow-up period through the participant's last six-month follow-up.
- Events related to planned treatments or physician visits for baseline conditions collected in the Medical History will not be collected unless there is an exacerbation of the condition.
- Any AE leading to withdrawal from the protocol will be collected throughout the study.
- All AEs related to changes in psychiatric status will be collected throughout the study.

AEs will be collected during introductory sessions and throughout Stage 1, Stage 2, and Stage 3, as well as associated cessation periods, on the Daily Diary. Information needed to determine severity and relatedness will be collected and confirmed by telephone contact conducted according to the Time & Events table. Each reported AE will be actively followed during follow-up phone calls or weekly visits until resolution. AEs will be recorded in the respective AE log eCRF based on onset date, e.g. an AE reported during Introductory Session 1 or the Stage 1 self-administration period would be recorded on the Stage 1 AE log eCRF. CIs or qualified site staff are responsible for review of safety data.

A Memory Aid Card will be provided to the subject on the last visit prior to the six-month follow-up to record information on medications taken to treat SAEs, AEs leading to withdrawal and psychiatric AEs during the follow-up period between the end of self-administration and the six-month follow-up evaluation. The Memory Aid Card will not be collected, but information from the card will be used to aid the participants in providing information to site staff. This information may be collected by phone.

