9.0 Collection of Concomitant Medications and Therapies

Information about all concomitant prescription medications, and only over the counter (OTC) medications associated with an AE, will be collected from screening up to the day of the final study visit in Cessation 2 or Stage 3, as applicable, including reasons for use, date started, date ended and dose information if available. During the follow-up period after this visit and before the six-month follow-up, information on new psychiatric medications will be gathered on the day of the six-month follow up study visit. During the follow-up period, healthcare utilization associated with AEs requiring medical attention and psychiatric AEs will be collected. Medications recorded per protocol, including medications taken to treat AEs, will be recorded on a concomitant medications form eCRF. Information on participation in evidence-based psychotherapy for PTSD will be collected throughout the study. Therapies and healthcare utilization recorded per protocol will be recorded on a concomitant therapies form eCRF.

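### Section 12.0 analyses adverse events by concomitant medication use, a factor that the Section 9.0 recording rule lets adverse events partly create

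*Protocol*

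**What the plan says.** Protocol Section 12.0 (Data Analysis) commits to the analysis: "Statistical analyses will be conducted to evaluate safety and AEs by marijuana treatment condition" and by a set of participant characteristics, given as "individual demographic characteristics (e.g. gender, history of cannabis use, concomitant medication/drug use, baseline CAPS-5 score". Gender, cannabis history and baseline CAPS-5 score are fixed before treatment. Nothing in the section restricts the medication item to use at baseline or before the event.

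Section 5.1.2 (Safety Measures) says where the medication data come from: "Concomitant medications and therapies will be collected as described in Section 9.0 of the protocol". Section 9.0 then sets two rules:

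- What is collected: "Information about all concomitant prescription medications, and only over the counter (OTC) medications associated with an AE, will be collected from screening", continuing to the last visit of Cessation 2 or Stage 3. Reasons for use and start and end dates are part of the record.
- Where it goes: "Medications recorded per protocol, including medications taken to treat AEs, will be recorded on a concomitant medications form eCRF".

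The AE window in Section 8.3 overlaps the medication window: "All AEs will be collected from enrollment until end of the active study period".

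There is a second source. The Daily Diary in Section 5.1.3 asks about "the daily amount of marijuana used concomitant use of alcohol, medications, or other drugs, as well as AEs", and attaches no AE condition to the medication question.

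**The concern.** A subgroup factor in a safety analysis should not depend on the safety outcome. Under Section 9.0, a participant who takes an OTC painkiller without an AE leaves no entry on the medication form, while one who takes the same painkiller for a headache reported as an AE does. A prescription medicine started to treat an AE also counts. If the factor is taken from that form, participants with AEs are moved into the user group because they had AEs.

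The likely misreading is a drug-interaction signal: participants on other medicines appear to tolerate marijuana worse. Section 7.2 lets participants stay on their medications and Section 2.1 says the trial is to inform larger trials, so such a signal could be carried forward.

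**Working it through.** The protocol states no figure for this analysis, so there is none to reproduce. The check asks how large an association the recording rule creates when medication truly has no relation to AEs.

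**Inputs from the protocol.** N=76 (Sections 4.2 and 5.3) and the 5% significance level (Section 12.0; two-sided assumed).

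**Assumed inputs; the protocol gives none of these.**
- a = probability that a participant has an AE.
- m = probability of having a medicine on record for reasons unrelated to AEs.
- t = probability that a participant with an AE has a medicine recorded because of it.

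**Step 1: the built-in odds ratio.**
- P(user | AE) = 1 − (1 − m)(1 − t)
- P(user | no AE) = m
- The odds ratio simplifies to OR = 1 + t / [m(1 − t)]

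This does not depend on a, and it exceeds 1 whenever t > 0. The direction is therefore fixed and only the size depends on the assumptions.

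| m | t | P(user given AE) | P(user given no AE) | OR |
|---|---|---|---|---|
| 0.7 | 0.10 | 0.730 | 0.70 | 1.16 |
| 0.5 | 0.25 | 0.625 | 0.50 | 1.67 |
| 0.3 | 0.50 | 0.650 | 0.30 | 4.33 |

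**Step 2: AE rates as the analysis would show them**, with a = 0.6 and m = 0.5.
- t = 0.2: users 0.36/0.56 = 64%, non-users 0.24/0.44 = 55%, risk ratio 1.18.
- t = 0.3: users 0.39/0.59 = 66%, non-users 0.21/0.41 = 51%, risk ratio 1.29.
- t = 0.5: users 0.45/0.65 = 69%, non-users 0.15/0.35 = 43%, risk ratio 1.62 (rounded up from 1.615).

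**Step 3: false-positive rate at N=76 by simulation.**
- Chi-square test, a = 0.6, m = 0.5: 14%, 26% and 61% for t = 0.2, 0.3 and 0.5, against 5% when t = 0.
- Same test, t = 0.3: 44% at m = 0.3 and 15% at m = 0.7. With m = 0.5 it is 22%, 20% and 15% at a = 0.3, 0.8 and 0.9.
- Fisher's exact test, a = 0.5, m from 0.3 to 0.7, t from 0.1 to 0.5: from about 4% (m = 0.7, t = 0.1) to 84% (m = 0.3, t = 0.5), and 15% at m = 0.5, t = 0.25. Fisher's test is conservative, so the 4% should be set against its own level with an uncontaminated factor (below).

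**Step 4: does the Daily Diary remove the problem?** Suppose all OTC use is captured, with 30% background use (assumed), and AE treatments still count. Then m is replaced by m′ = 1 − (1 − m)(0.7). At m = 0.5, m′ = 0.65, and with t = 0.25 the OR is 1 + 0.25/(0.65 × 0.75) = 1.51, down from 1.67. Over the same grid the Fisher false-positive rate is about 4% to 56%. The bias is smaller but still present.

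**Step 5: after the fix.** With the factor limited to baseline medicines, t = 0 and the OR is 1. The Fisher rejection rate is 2.6% to 4.0% across the grid.

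**The case against.** The strongest case against has five parts.

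1. *The protocol does not say that a user is anyone with an entry on the medication form.* The list is introduced as examples of demographic characteristics, the other three are pre-treatment, and a statistical analysis plan (not shown) may define the factor as pre-existing use. That reading is possible. But the protocol uses a term that it defines elsewhere by a post-baseline, AE-dependent rule. An analysis plan that follows the two sections as written inherits the bias.

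2. *The record does not depend wholly on AEs.* This stands. All prescription medicines are recorded, the diary asks about medicines unconditionally, and the drug-use half of the item is not touched by the OTC rule. A reader might infer that a medication record exists only when an event exists. That is true only of OTC entries on the Section 9.0 form, not of the factor as a whole.

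3. *AE treatments can be identified.* This stands too. Section 9.0 collects start dates and reasons for use, so the data support a clean definition. The fault lies in the stated factor, not in data that cannot be recovered.

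4. *The size is assumed.* Correct. Section 8.1 counts common drug effects such as dry mouth as expected AEs, so the AE rate may be high. At a = 0.9 (assumed) with m between 0.5 and 0.8, t = 0.2 gives a risk ratio of 1.03 to 1.04 and 7% to 9% false positives. At t = 0.5 the false-positive rate is still 18% to 33%. A reader might infer that the analysis is bound to report more AEs among users, but with a = 0.6, m = 0.5 and t = 0.2 about 86% of trials would show no significant difference.

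5. *Comparisons between products within user and non-user strata.* One might infer that these are distorted as well. Section 12.0 does not clearly plan such comparisons, so the point is not pressed.

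**Conclusion.** The point holds as a contamination problem. As written, Sections 9.0 and 12.0 let AEs partly define a factor by which AEs are then compared, and the bias is always towards more AEs among medication users. Counting AE treatments is enough to create it; the OTC rule adds to it.

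The size cannot be fixed from the documents. Under the assumed rates, the false-positive rate of a nominal 5% test at N=76 runs from about the nominal level to over 60%, depending mainly on how often AEs lead to a recorded medicine and how many participants are on record anyway.

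This is a supportive safety analysis in a self-described pilot. The documents give no ground for extending the concern to the primary CAPS-5 endpoint or to AEs by randomised condition. The change is worth making because it is cheap, but the trial's main conclusions do not rest on it.

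**What to change.** In Section 12.0, replace the concomitant medication/drug item with medication and drug use at baseline, defined as:

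- prescription medicines ongoing before the first introductory session (Section 9.0 collects these from screening, with start dates); and
- substance use from the 90-day timeline follow-back at screening (Section 5.1.2).

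State that medicines taken to treat an AE, identified from the recorded start dates and reasons for use, do not define the factor and are only tabulated. Stop describing medication use as a demographic characteristic.

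**Cost.** A sentence or two in Section 12.0 or the analysis plan, and no new data collection. There is a small loss: a baseline-only factor says nothing about medicines started during the study. If those are of interest, add a secondary time-ordered analysis restricted to prescription medicines started before AE onset. OTC medicines should stay out of it, because the Section 9.0 form holds them only where an AE is involved.
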